### 8.1.2 Adverse Drug Reaction

An adverse drug reaction (ADR) is a response to a medicinal product which is noxious and unintended. Response in this context means that a causal relationship between a medicinal product and an adverse event is at least a reasonable possibility. This includes adverse reactions which arise from: use of a medicinal product within the terms of the marketing authorization; use outside the terms of the marketing authorization, including overdose, misuse, abuse and medication errors; and occupational exposure\*.

\* This corresponds to the exposure to a medicinal product for human use as a result of one's occupation, such as nurses who may handle products routinely in their occupational setting.

### 8.1.3 Serious Adverse Event Definition

An adverse event or suspected adverse reaction is considered "serious" if, in the view of either the investigator or the sponsor, it results in any of the following outcomes:

- Death
- A life-threatening adverse drug experience – any adverse experience that places the patient, in the view of the initial reporter, at immediate risk of death from the adverse experience as it occurred. It does not include an adverse experience that, had it occurred in a more severe form, might have caused death.
- Inpatient hospitalization or prolongation of existing hospitalization
- A persistent or significant incapacity or substantial disruption of the ability to conduct normal life functions.
- A congenital anomaly/birth defect.

Important medical events that may not result in death, be life-threatening, or require hospitalization may be considered a serious adverse drug experience when, based upon appropriate medical judgment, they may jeopardize the patient or subject and may require medical or surgical intervention to prevent one of the outcomes listed in this definition. Examples of such medical events include allergic bronchospasm requiring intensive treatment in an emergency room or at home, blood dyscrasias or convulsions that do not result in inpatient hospitalization, or the development of drug dependency or drug abuse (21 CFR 312.32).

It is the responsibility of the PI and the research team to ensure serious adverse events are reported according to the Code of Federal Regulations, Good Clinical Practices, the protocol guidelines, the sponsor's guidelines, and Institutional Review Board policy.

## 8.2 Procedures for Reporting Serious Adverse Events

AEs may be spontaneously reported by the patient and/or in response to an open question from study personnel or revealed by observation, physical examination, or other diagnostic procedures. Any clinically relevant deterioration in laboratory assessments or other clinical finding is considered an AE. When possible, signs and symptoms indicating a common underlying pathology should be noted as one comprehensive event. For serious AEs, the investigator must determine both the intensity of the event and the relationship of the event to study drug administration.

AEs which are serious must be reported to Millennium Pharmacovigilance (or designee) from the first dose of study drug through 30 days after administration of the last dose of ixazomib. Any SAE that occurs at any time after completion of ixazomib treatment or after the designated follow-up period that the sponsor-investigator and/or sub-investigator considers to be related to any study drug must be reported to Millennium Pharmacovigilance (or designee). In addition, new primary malignancies that occur during the follow-up periods must be reported, regardless of causality to study regimen, for a minimum of three years after the last dose of the investigational product, starting from the first dose of study drug. All new cases of primary malignancy must be reported to Millennium Pharmacovigilance (or designee). Active follow up for detection of second primary malignancies beyond the planned study is not required; however, if the sponsor-investigator learns about the occurrence of a second primary malignancy in one of the study patients within 3 years after the last study drug administration he must report the event to Millennium Pharmacovigilance (or designee).

Planned hospital admissions or surgical procedures for an illness or disease that existed before the patient was enrolled in the trial are not to be considered AEs unless the condition deteriorated in an unexpected manner during the trial (e.g., surgery was performed earlier or later than planned). All SAEs should be monitored until they are resolved or are clearly determined to be due to a patient's stable or chronic condition or intercurrent illness(es).

The principal investigator, [name] MD also referred to as the sponsor-investigator, is responsible for reporting serious adverse events (SAEs) to any regulatory agency and to the sponsor- investigator's EC or IRB.

Regardless of expectedness or causality, all SAEs (including serious pretreatment events) must also be reported in English to Millennium Pharmacovigilance (or designee):

**Fatal and Life Threatening SAEs** within 24 hours of the sponsor-investigator's observation or awareness of the event

**All other serious (non-fatal/non-life threatening) events** within 4 calendar days of the

sponsor-investigator's observation or awareness of the event

See below for contact information for the reporting of SAEs to Millennium Pharmacovigilance.

The sponsor-investigator must fax or email the SAE Form per the timelines above. A sample of an SAE Form will be provided.

The SAE report must include at minimum:

- **Event term(s)**
- **Serious criteria**
- **Intensity of the event(s):** Sponsor-investigator's or sub-investigator's determination. Intensity for each SAE, including any lab abnormalities, will be determined by using the NCI CTCAE version specified in the protocol, as a guideline, whenever possible. The criteria are available online at <http://ctep.cancer.gov/reporting/ctc.html>.
- **Causality of the event(s):** Sponsor-investigator's or sub-investigator's determination of the relationship of the event(s) to study drug administration.

Follow-up information on the SAE may be requested by Millennium.

Intensity for each SAE, including any lab abnormalities, will be determined by using the NCI CTCAE version used at your institution, as a guideline, whenever possible. The criteria are available online at <http://ctep.cancer.gov/reporting/ctc.html>.

In the event that this is a multisite study, the sponsor-investigator is responsible to ensure that the SAE reports are sent to Millennium Pharmacovigilance (or designee) from all sites participating in the study. Sub-investigators must report all SAEs to the sponsor-investigator so that the sponsor-investigator can meet his/her foregoing reporting obligations to the required regulatory agencies and to Millennium Pharmacovigilance, unless otherwise agreed between the sponsor-investigator and sub-investigator(s).

Relationship to all study drugs for each SAE will be determined by the investigator or sub-investigator by responding yes or no to the question: Is there a reasonable possibility that the AE is associated with the study drug(s)?

Sponsor-investigator must also provide Millennium Pharmacovigilance with a copy of all communications with applicable regulatory authorities related to the study product(s), as soon as possible but no later than 4 calendar days of such communication.

**8.3 Procedures for Reporting Drug Exposure During Pregnancy and Birth Events**

If a woman becomes pregnant or suspects that she is pregnant while participating in this study or within 90 days after the last dose, she must inform the investigator immediately and permanently discontinue study drug. The sponsor-investigator must immediately fax a completed Pregnancy Form to the Millennium Department of Pharmacovigilance or designee (see Section 8.2). The pregnancy must be followed for the final pregnancy outcome.

If a female partner of a male patient becomes pregnant during the male patient's participation in this study, the sponsor-investigator must also immediately fax a completed Pregnancy Form to the Millennium Department of Pharmacovigilance or designee (see Section 8.2). Every effort should be made to follow the pregnancy for the final pregnancy outcome.

Suggested Pregnancy Reporting Form:

- Pregnancy Report Form (provided by Millennium)

## **9. ADMINISTRATIVE REQUIREMENTS**

### **9.1 Data Collection**

Data for the study will be collected and entered in RedCap database and in CORE.

### **9.2 Data Confidentiality Plan**

To maintain patient confidentiality, all information will be de-identified and only labeled with a sponsor provided deidentified random number key. A confidential list will be created that links the code to the subject's name. However, patient confidentiality will be strictly maintained at all times. Only authorized people (PI, delegated research staff) will have access to the list of names. The data and the confidential list of coded names will be kept securely at MD Anderson / Red Cap database and password protected behind the institutional firewall. This information is expected to lead to publication and confidentiality will be maintained throughout the analysis. No individual patient will be identified in any published or presented data, only summary data will be used. All paper files containing data will be destroyed per MDACC policy on medical records retention and destruction within 5 years after study publication. Electronic data will not be destroyed after 5 years as electronic data on MDACC servers is stored indefinitely.

### **9.3 Product Complaints**

A product complaint is a verbal, written, or electronic expression that implies dissatisfaction regarding the identity, strength, purity, quality, or stability of a drug product. Individuals who identify a potential product complaint situation should immediately contact Millennium (see below) and report the event. Whenever possible, the associated product should be maintained in accordance with the label instructions pending further guidance from a Millennium Quality representative.

A medication error is a preventable event that involves an identifiable patient and that leads to inappropriate medication use, which may result in patient harm. While overdoses and underdoses constitute medication errors, doses missed inadvertently by a patient do not. Investigators must record all medication errors (including overdose) on the appropriate CRF form. Individuals who identify a potential medication error situation should immediately contact Takeda (see below) and report the event.

**For Product Complaints, or Medication Errors (Including Overdose), contact Takeda  
Pharmacovigilance**

## 11. APPENDICES

### 11.1 Eastern Cooperative Oncology Group (ECOG) Scale for Performance Status

Grade	Description
0	Normal activity. Fully active, able to carry on all predisease performance without restriction
1	Symptoms but ambulatory. Restricted in physically strenuous activity, but ambulatory and able to carry out work of a light or sedentary nature (e.g., light housework, office work)
2	In bed < 50% of the time. Ambulatory and capable of all self-care, but unable to carry out any work activities. Up and about more than 50% of waking hours.
3	In bed > 50% of the time. Capable of only limited self-care, confined to bed or chair more than 50% of waking hours.
4	100% bedridden. Completely disabled. Cannot carry on any self-care. Totally confined to bed or chair
5	Dead

Source: Oken MM, Creech RH, Tormey DC, Horton J, Davis TE, McFadden ET et al. Toxicity and response criteria of the Eastern Cooperative Oncology Group. Am J Clin Oncol 1982; 5 (6):649-55.

## 11.2 Cockcroft-Gault Equation

For males:

$$\text{Creatinine Clearance} = \frac{(140 - \text{age}[\text{years}]) \times \text{weight} [\text{kg}]}{72 \times (\text{serum creatinine}[\text{mg/dL}])} \quad \text{OR} \quad \frac{(140 - \text{age}[\text{years}]) \times \text{weight} [\text{kg}]}{0.81 \times (\text{serum creatinine}[\mu\text{mol/L}])}$$

For females:

$$\text{Creatinine Clearance} = \frac{0.85 (140 - \text{age}[\text{years}]) \times \text{weight} [\text{kg}]}{72 \times (\text{serum creatinine}[\text{mg/dL}])} \quad \text{OR} \quad \frac{0.85 (140 - \text{age}[\text{years}]) \times \text{weight} [\text{kg}]}{0.81 \times (\text{serum creatinine}[\mu\text{mol/L}])}$$

Source: Cockcroft DW, Gault MH. Prediction of creatinine clearance from serum creatinine. Nephron 1976;16(1):31-41.

==

**11.3 SCHEDULE OF STUDY ASSESSMENTS**

Days (+/-3d)	Screening A	C1D1	C2D1	C3D1	C4D1	C5D1	C6D1	C7D1	C8D1	C9D1	C10D1	C11D1	C12D1	C13D1	C14D1	C15D1+	EOS (+/- 7 days)
Informed consent, review inclusion/exclusion, general medical history B	X																
Vital signs, weight and height	X	X	X	X	X	X	X	X	X	X	X	X	X	X	X	X	X
ECOG and B symptoms C	X	X	X	X	X	X	X	X	X	X	X	X	X	X	X	X	X
Physical Exam D	X	X	X	X	X	X	X	X	X	X	X	X	X	X	X	X	X
12 lead ECG and ECHO E	X																
PET/CT or CT scan F	X				X F				X F				X F			X F	X F
Bone marrow biopsy/aspirate G	X				X G				X G							X G	X
MRD assessment H	X				X H				X H							X H	X
Tumor biopsy	X																X
CBC, CMP, and Hepatitis Testing i,j	X	X	X	X	X	X	X	X	X	X	X	X	X	X	X	X	X J

Days (+/-3d)	Screening A	C1D1	C2D1	C3D1	C4D1	C5D1	C6D1	C7D1	C8D1	C9D1	C10D1	C11D1	C12D1	C13D1	C14D1	C15D1	
Quantitative Immunoglobulins	X																
Pregnancy Test	X																

Footnotes Table of Assessments

- A. Perform within 28 days prior to cycle 1 day 1. Assessments performed as standard of care may be used for screening. *BIOPSY TISSUES* obtained up to 8 weeks prior to start of C1D1 can be used as long as we have enough tissue for analysis.
- B. Written informed consent form(s) must be signed by the patient before any study specific procedures are performed.
- C. B symptoms: Unexplained weight loss>10% over previous 6 months, fever (>38C) and/or drenching night sweats.
- D. Complete physical exam at screening, including cardiovascular, respiratory, abdominal, lymph node, skin ENT, extremities and endocrinological examination. Targeted physical exams at subsequent visits, limited to systems of clinical relevance, (i.e., cardiovascular, respiratory, lymph nodes, liver, and spleen), and dose systems associated with clinical signs/symptoms.
- E. Single 12-lead ECG and Echo is required at screening. If clinically significant abnormality is noted by the attending physician, a referral to cardiology will be made.
- F. CT scans must include neck, chest, abdomen, pelvis and include oral and IV contrast. PET/CT performed at screening, at the end of Cycle 4, at the end of cycle 8, at the end of Cycle 15, and at the End of Study visit if not performed within the last 2 months. After Cycle 15, CT scans will be performed every 4 months. If PET/CT is performed and includes a CT scan of sufficient diagnostic quality and provides bidimensional nodal and liver and spleen measurements, an additional dedicated CT is not required at the time point. MRI may be used in place of CT at investigator's discretion.
- G. Bone marrow biopsies/aspirates at specified time points are mandatory (Screening, at the end of cycle 4, at the end of cycle 8, at the end of Cycle 15, and at the End of Study visit ) unless shown to be clear on previous examination by multi flow cytometry minimum sensitivity 10-4. \* If patient has progression on the study, we do require Bone marrow biopsy/aspiration at progression. For example, if week 9 imaging study shows clear progression beyond a reasonable doubt, we would like to perform a bone marrow biopsy/aspiration for end of study.
- H. Minimal residual disease assessment by ASO PCR in mantle cell lymphoma patients and flow cytometry. Peripheral blood will be collected from all patients as well as bone marrow aspirates in those patients required to undergo bone marrow aspirate and biopsy will be collected at Screening, at the end of cycle 4, at the end of cycle 8, at the end of cycle 15, and at the End of Study visit. Collect 20 mL's of blood in EDTA and 5 mL of a bone marrow aspirate in EDTA. Transport within 4 hours at room temperature to appropriate laboratory.

- I. Blood chemistry: Sodium, potassium, chloride, BUN, creatinine, glucose, calcium, total protein, albumin, AST, ALT, alkaline phosphatase, total bilirubin, LDH, phosphate, uric acid, magnesium and bicarbonate.
- J. Hepatitis C antibody, hepatitis B surface antigen and hepatitis B core antibody will be evaluated. If hepatitis B core antibody or hepatitis B surface antigen or Hepatitis C antibody is positive, then PCR to quantitate hepatitis B DNA or hepatitis C RNA must be performed. DNA PCR needs to be confirmed negative (<29 U) prior to enrollment in subjects who are hepatitis B core antibody or hepatitis B surface antigen positive. For subjects who are hepatitis C antibody positive, hepatitis C PCR needs to be confirmed negative prior to enrollment. Hepatitis testing does not need to be repeated at the End of Study visit.

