## **3. STUDY ENDPOINTS**

### **3.1 Primary Endpoints**

Complete remission rate of BTK inhibitor refractory MCL patients with ixazomib and rituximab at 16 weeks of therapy.

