### **3.2 Secondary Endpoints**

ORR as assessed by Lugano criteria (2014) at 16 weeks, TTR, PFS and OS

Safety and tolerability at completion at weeks 8, 16, 28, 42 and 56 weeks. Toxicities will/ be measured using CTCAE v4.0.

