## 6.4 Dose-Modification Guidelines

### 6.4.1 Recommended Ixazomib Criteria for Beginning or Delaying a Subsequent Treatment Cycle & Dose Modifications for Treatment Associated Toxicity

Treatment with ixazomib will use a cycle length of 28 days. For a new cycle of treatment to begin, the patient must meet the following criteria:

- ANC must be  $\geq 1,000/\text{mm}^3$ .
- Platelet count must be  $\geq 50,000/\text{mm}^3$ .
- All other nonhematologic toxicity (except for alopecia) must have resolved to  $\leq$  Grade 1 or to the patient's baseline condition

If the patient fails to meet the above-cited criteria for initiation of the next cycle of treatment, dosing should be delayed for 1 week. At the end of that time, the patient should be re-evaluated to determine whether the criteria have been met. If the patient continues to fail to meet the above-cited criteria, delay therapy and continue to reevaluate. The maximum delay before treatment should be discontinued will be 3 weeks or at the discretion of the Principal Investigator.

For dosing recommendations upon recovery, refer to Table 6-2 and Table 6-3.

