## **7. STATISTICAL AND QUANTITATIVE ANALYSES**

### **7.1 Statistical Methods**

**Primary endpoint:** complete response rate at 16 weeks measured using Lugano (2014)

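### The schedule grid places the week-16 response assessment at C4D1 (week 12), four weeks before the primary endpoint, and no window or rule for delayed cycles is given

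*Combined protocol and SAP*

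**What the plan says.** Section 3.1 defines the primary endpoint as "Complete remission rate of BTK inhibitor refractory MCL patients with ixazomib and rituximab at 16 weeks of therapy". Sections 7.1 and 7.1.1 repeat week 16, and Section 7.1.1 sets the design CR rate of 30% at that time. No section gives a window for the reading.

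Section 6.4.1 fixes the cycle: "Treatment with ixazomib will use a cycle length of 28 days". If the criteria for starting a new cycle are not met, "dosing should be delayed for 1 week", with re-evaluation after that. The maximum is 3 weeks or as the Principal Investigator decides.

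The grid in Section 11.3 has one column per cycle Day 1, under a header window of 3 days either side. The row "PET/CT or CT scan" is marked at screening, C4D1, C8D1, C12D1, C15D1+ and end of study. The marrow and MRD rows are marked at the same times except C12D1. C5D1 has no mark in any of the three rows.

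Footnote F reads "PET/CT performed at screening, at the end of Cycle 4, at the end of cycle 8, at the end of Cycle 15", and adds the end-of-study visit. Footnotes G (marrow) and H (MRD) use the same ends of cycles, as does Section 7.1.7 for the immune and MCL profile. No text says whether the grid or the footnotes govern.

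**The concern.** The primary endpoint is read from the assessment that the grid puts at C4D1. A scan there follows three cycles of treatment. A scan at the end of cycle 4 follows four. With 24 patients a few remissions decide how the result compares with the 10% historical rate in Section 7.1.1, so the scan date has to be unambiguous.

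Two things are unclear. First, the grid and its own footnotes differ by a whole cycle. Second, even under the footnotes the scan is tied to cycles while the endpoint is stated in weeks. The two separate as soon as a cycle starts late.

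The futility rule in Section 7.1.9 is also anchored to a first restaging at week 16, so an earlier scan would change when early progression is found.

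**Working it through.** **The plan's own figure.** Section 7.1.1 gives a lower 95% bound of 0.12 for a 30% CR rate with N = 24. The Wald bound is 0.30 − 1.96 × √(0.30 × 0.70 / 24) = 0.117, which rounds to 0.12. The exact bound, the method named in Section 7.1.6, is 0.126 for 7/24. The figure stands, and this point does not dispute it.

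**Grid columns.** The header and the imaging row each have 18 fields. Counted field by field, the marks fall in the columns listed above, so the C4D1 placement is not a table-reading artefact.

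**Timing without delays.** CxD1 is study day (x − 1) × 28 + 1, with (x − 1) × 4 weeks elapsed. The end of cycle x is day 28x, week 4x.

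| Cycle | Day 1 of cycle | End of cycle |
|---|---|---|
| 4 | day 85, week 12 | day 112, week 16 |
| 5 | day 113, week 16 | day 140, week 20 |
| 8 | day 197, week 28 | day 224, week 32 |
| 12 | day 309, week 44 | day 336, week 48 |
| 15 | day 393, week 56 | day 420, week 60 |

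The C4D1 window is days 85 ± 3 = 82 to 88. The same window around the end of cycle 4 is days 112 ± 3 = 109 to 115. The nearest edges are 109 − 88 = 21 days apart.

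**Timing with delays.** The end of cycle 4 falls at week 16 plus the total delay before cycles 2, 3 and 4.
- One 1-week delay: week 17.
- A 3-week delay before each of the three cycles: 16 + 3 × 3 = week 25. This is an extreme case, and not a strict limit because of the investigator's discretion.
- C4D1 itself moves from week 12 to between weeks 12 and 21 (12 + 3 × 3) on the same assumption.

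**What an early reading could do (assumed rates).** The documents give no week-12 CR rate, so the rates below are assumptions. Seven remissions is the smallest count whose exact lower bound exceeds 10% (6/24: 0.098; 7/24: 0.126). If all 24 patients are read at week 12 and the week-16 rate is 30%:

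| Assumed week-12 CR rate | Expected CRs of 24 | Chance of at least 7 |
|---|---|---|
| 30% (no difference) | 7.2 | 61% |
| 25% | 6.0 | 39% |
| 20% | 4.8 | 19% |

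**The case against.** The strongest reply is that the footnote governs. The on-treatment marks carry the footnote letters, footnotes F, G and H agree with each other and with Section 7.1.7, and the end of cycle 4 is exactly week 16 when nothing is delayed. Since the grid has only Day 1 columns, a mark under cycle 4 could be shorthand for that cycle. This is the likelier intention, and it means the conflict is the grid against everything else. A reader might infer three competing times, but the documents do not support that.

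It does not remove the defect. The grid carries an explicit 3-day window on C4D1, and nothing tells staff to override it. Footnote F is also not a full key to the grid: the C12D1 mark carries its letter, yet the footnote lists no cycle 12 scan.

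Other stronger readings also fail:
- Different sites might be thought to follow different readings and have their results pooled. Section 4.1 describes a single-center trial. The risk is inconsistent reading within one team.
- Section 3.2 lists "Safety and tolerability at completion at weeks 8, 16, 28, 42 and 56 weeks", and weeks 28 and 56 match C8D1 and C15D1. That might suggest that the grid is right throughout. These are tolerability times, and week 16 in the same list matches the end of cycle 4.
- The C12D1 mismatch might be read as a 28-week scan gap (week 32 to week 60). The row allows a CT, while the footnote sentence lists PET/CT times, so the C12D1 mark may be a CT.

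Tying the reading to four delivered cycles is also defensible. The objection here is that the plan does not choose.

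**Conclusion.** The contradiction is real and should be corrected. Read literally, the grid takes the only primary endpoint at week 12, 4 weeks before the time in Sections 3.1, 7.1 and 7.1.1, and its window cannot close the gap. Read by the footnotes, the assessment is at week 16 only if cycles 2 to 4 all start on time. It moves to week 17 after one 1-week delay, and to week 25 if each of those three cycles starts 3 weeks late. No window or delay rule covers this.

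The timing result rests only on the 28-day cycle and the grid as printed. A bias in the CR rate is not shown: the fall in the chance of at least 7 remissions from 61% to between 19% and 39% depends on assumed week-12 rates of 20% to 25%, and if the rate is already 30% at week 12 nothing changes.

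**What to change.** 1. Move the C4D1 imaging, marrow and MRD marks to a week-16 column: day 113 from C1D1, that is, the end of cycle 4 and before C5D1 dosing. State a window, for example 7 days either side (days 106 to 120). That would absorb a single 1-week delay but not longer ones.
2. State whether the week-16 CR reading is timed from first dose or from cycles when cycles are delayed. Timing from first dose matches the endpoint as worded.
3. Reconcile the C8D1, C12D1 and C15D1 marks with footnotes F to H, choosing grid or footnote for each. The C15D1 mark should not be moved automatically to the end of cycle 15: that is week 60, while Section 3.2 and the note on continuing ixazomib in Section 11.3 use week 56. For cycle 12, say in footnote F which scan is meant.
4. Reconcile the 8-week restaging in Section 4.1 with Section 7.1.9, which calls week 16 the first restaging. The grid has no week-8 scan.

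The cost is a correction to the schedule table and a sentence or two of text, with no extra week-16 scan. The one downside of timing from first dose is that a delayed patient may have had fewer than four full cycles when scanned.
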